#### ***HCS-CES Procedure***

As discussed previously, data will be collected across the five campaigns in Wave 1 communities with annual inclusion of Wave 2 communities for comparison purposes. Wave 1 communities will also be included in a follow-up CEQ to measure sustainability of knowledge, attitudes and behaviors and Wave 2 communities will receive a CEQ to measure the overall impact of the campaigns across the year of implementation. These data collection points represent our cross-sectional study design. The following sections describe the data collection process for the first campaign for Wave 1 communities; these procedures will then be repeated for the second campaign for Wave 1, as well as for campaigns 3, 4, and 5.

#### Details of proposed survey of attitudes regarding stigma, naloxone availability, and MOUD for each discrete campaign

***Campaign Evaluation Questionnaire:*** For the proposed community survey, the Facebook advertisements will target individuals living in the geographic regions of all 67 HCS communities. The survey will be programmed to continue until the number of desired completions has been achieved. Each discrete CEQ will be staggered to serve as both pretest for the beginning campaign and posttest for each previous campaign as test messages from all previous campaigns will be iteratively added to each subsequent CEQ. This will provide an overall impression of message recognition from each previous campaign (via cued recall of messages used in each previous campaign) as well as the current campaign.

The CEQ includes measures of stigma toward individuals with OUD and EBPs to prevent or treat OUD, as well as awareness and intentions to seek MOUD and OEND. Using a cued-recall survey methodology (discussed as follows), respondents will also be asked questions about recognition and attitudes toward other competing campaign messages being disseminated in their community. They will not be shown HCS messages at baseline. Survey completion is estimated to require approximately 20 minutes. Individuals will be asked if they are willing to be

re-contacted for the second and third time points of the campaign currently running in their community, and if willing, to provide an email address to help construct the cohort panel discussed previously. This process will be duplicated for all subsequent Campaign Evaluation Questionnaires.

The basic procedure for the cued-recall survey methodology involves two steps. Participants will first answer a set of demographic questions and items that assess their beliefs about evidence-based treatments for OUD, stigma surrounding OUD and treatments for it, and attitudes toward individuals with OUD. After completing these sections, each participant will be shown the current HCS messages being disseminated in their community, an additional message from non-HCS campaigns currently running in their state (e.g., sponsored by a federal, state, or non-profit organization), and a foil (or fabricated) message that will aid with calculating alternative explanations for message exposure effects. After each message, the participants will complete brief measures using the Message Impact Framework (MIF) to assess the perceived effectiveness of the messages, recognition of the messages, and frequency of self-reported exposure to the messages. We intend to submit these test messages to the sIRB as they are finalized and produced.

The data will be aggregated to the community level and aggregated for all individuals recruited in a given community. RSs have the option to conduct site-specific analyses so that they can share and give back non-identifying CEQ data to their HCS communities.

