(OEND), and the acceptability of MOUD treatment in the Wave 1 and Wave 2 communities (see Figure 9 for a timeline and visual representation of data collection points for the HCS-CES community surveys). Survey data will be collected from a sample generated from social media recruitment (Facebook). In addition, participants may opt in to be part of a longitudinal panel in which they are surveyed at each time point. These changes will be assessed across communities using differences between treatment and control communities and within communities over time by dose-response effects associated with exposure to campaign messages and other messages in the community environment. See *Campaign Evaluation Questionnaire*.

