3	How will respondents be selected?	Potential participants may be approached by a coalition member or will respond to an open solicitation via social media and newspaper items. They will be screened for (1) being between ages 18 and 75 and (2) being a resident of the town or county where the groups will take place. The RSs will attempt to have a broad mix of demographic backgrounds and people from different occupation groups in each group (e.g., not all working in the health sector but also representing connections to public safety, law enforcement, business/retail, farming, and other sectors).
4	Sample size	Total up to 400 across 33 Wave 1 communities
5	Repeated (Y/N)	Yes
	If yes: frequency (e.g., annually, monthly)	These focus groups may be repeated for subsequent communication campaigns but will not include the same participants
6	Mode (telephone, web, in person)	In person or telephone, to be determined by each RS
7	Self-administered or interviewer administered	Interviewer administered
8	Informed consent (verbal, written, digital)	Verbal or written
9	Incentives (Y/N)	Yes
	If yes: incentive type (e.g., gift card, cash, check)	\$50–\$75 gift card to be determined by the RS
10	Seeking Waiver of Documentation of Informed Consent (Y/N)	Yes
11	Cross-site or site specific (specify site)	Cross-site
12	Data collection platform (e.g., REDCap, video)	Audio-recording. These recordings will be saved on secure project servers and deleted after analysis is complete.
13	Audio-recording (Y/N)	Yes
14	Other respondent-facing material (e.g., email invitation to participate) (specify)	Email invitation, confirmation, and meeting logistics information

General Template Costing the Community Engagement Process (CAB Members)		
Main Study Data Collection		
1	Purpose	To collect the resources (e.g., labor, time, space, equipment) spent on CE activities by CAB members
2	Respondent	CAB members and other key informants
3	How will respondents be selected?	All CAB members attending the CAB meetings will be invited to participate
4	Sample size	60–80 CAB members (15–20 members per state * 4)
5	Repeated (Y/N)	Yes
	If yes: frequency (e.g., annually, monthly)	Monthly (or when CAB meetings are held)
6	Mode (telephone, web, in person)	In person, web, or telephone

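### The campaign survey can re-survey people it has already shown the campaign messages, and no rule separates them from first-time respondents when recognition and exposure are measured

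*Protocol*

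**What the plan says.** All of this is in Protocol Section 6.1.1.4, in the parts on the HCS Communication Campaign Evaluation Study.

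- **Re-entry.** The Overview recruits through social media and adds that "participants may opt in to be part of a longitudinal panel in which they are surveyed at each time point". The survey-details part is narrower: people are asked whether they may be "re-contacted for the second and third time points of the campaign currently running in their community". It then says: "This process will be duplicated for all subsequent Campaign Evaluation Questionnaires".
- **Messages shown.** After the belief and stigma items, "each participant will be shown the current HCS messages being disseminated in their community", together with one non-HCS message and a fabricated foil. Also, "test messages from all previous campaigns will be iteratively added to each subsequent CEQ". No HCS messages are shown at baseline. Table 7 agrees: message impact is measured at every CEQ except the initial one.
- **Aggregation.** "The data will be aggregated to the community level and aggregated for all individuals recruited in a given community". Nothing there mentions the panel.
- **Stated design.** The HCS-CES Procedure says: "These data collection points represent our cross-sectional study design". Community Survey Participants has each new sample complete the screener, and eligibility rests on age and residence.
- **Schedule.** CEQ1, 4, 6 and 7 run in both waves; CEQ2, 3 and 5 run in Wave 1 only.
- **Use of the measure.** HCS-CES H2 relates the number of messages recognised and reported exposure frequency to attitudes, at the level of the individual respondent. The Overview also plans dose-response analyses on message exposure.

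**The concern.** Recognition and reported exposure are meant to measure what the campaign delivered in the community. For a returning panel member, the survey has itself delivered the messages. Such a person can truthfully report having seen a message that reached them only through an earlier questionnaire.

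If returnees are pooled with new respondents, the predictors in HCS-CES H2 mix campaign exposure with survey exposure. If people who volunteer to return also hold more favourable attitudes, a positive association can appear without any campaign effect. If survey-created recognition is unrelated to attitudes, it dilutes a real association. In the dose-response analyses, the number of earlier showings rises with calendar time in Wave 1, so measured exposure can climb while real exposure does not.

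**Working it through.** **1. The plan's own sample size.** Inputs from Community Survey Participants: SD of paired change 0.09, correlation 0.95, change 0.05, ICC 0.01 to 0.05, 33 Wave 1 communities, two-sided 0.05, power 80%.

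- SD per person = 0.09/√(2(1−0.95)) = 0.2846. SD of change between independent people = 0.2846 × √2 = 0.4025, the stated 0.40.
- Variance of the mean change = 0.40²[1+(m−1)ICC]/(33m). With a noncentral t on 32 degrees of freedom, m = 20 at ICC 0.01 and 81 at ICC 0.05.

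This reproduces the stated 20 to 80 surveys per community, which is not disputed. It also shows that the calculation assumes different people at each time point, so returnees are outside its model.

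**2. Earlier message-showing CEQs** for a panel member surveyed every time, counted from the schedule and leaving out CEQ1:

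| At | Wave 1 | Wave 2 |
|---|---|---|
| CEQ4 | 2 | 0 |
| CEQ6 | 4 | at most 1 |
| CEQ7 | 5 | at most 2 |

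Four at CEQ6 is a maximum. It applies to Campaign 1 messages; later campaigns' messages can have been shown fewer times. The Wave 2 counts are upper limits because the Protocol does not make clear what Wave 2 respondents see at CEQ4 and CEQ6, before any campaign runs there. If they see no HCS messages, the Wave 2 count at CEQ6 is 0.

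**3. Possible size at CEQ6.** The documents give neither the share of returnees (f) nor the chance that one showing creates recognition (q). Both are assumptions here, as is true recognition r = 10% in both waves, and all returnees are taken to have been surveyed every time. With n earlier showings:

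measured recognition = r + f(1−r)[1−(1−q)ⁿ]

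Example, f = 25%, q = 30%, n = 4: 0.10 + 0.25 × 0.90 × (1 − 0.70⁴) = 0.10 + 0.225 × 0.7599 = 27.1%.

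| f | q | Wave 1 (n=4) | Wave 2 (n=1) | Gap, points | Gap if Wave 2 n=0 |
|---|---|---|---|---|---|
| 10% | 10% | 13.1% | 10.9% | 2.2 | 3.1 |
| 10% | 30% | 16.8% | 12.7% | 4.1 | 6.8 |
| 25% | 10% | 17.7% | 12.2% | 5.5 | 7.7 |
| 25% | 30% | 27.1% | 16.8% | 10.3 | 17.1 |
| 50% | 10% | 25.5% | 14.5% | 11.0 | 15.5 |
| 50% | 30% | 44.2% | 23.5% | 20.7 | 34.2 |

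With f = 0 every gap is zero. The last column is also the artificial rise within Wave 1 from CEQ2, where no earlier showing exists, to CEQ6.

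**4. Safeguards in the text.** The foil measures false recognition of a message nobody has seen; it cannot identify real messages seen in an earlier questionnaire. Asking beliefs and stigma before showing messages protects those items within one questionnaire, but not from showings at earlier ones.

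**The case against.** The best defence is that the plan intends fresh cross-sectional samples plus a separate cohort. The Overview introduces the panel as an addition, the screener is for each new sample, and the design is called cross-sectional. The aggregation sentence is general. This reading is possible, and it is why the text should be reconciled rather than called simply wrong. But no passage says the panel will be analysed separately or kept out of the recognition measure. The narrower re-contact wording also does not remove the problem, because the offer is renewed at every CEQ.

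Four stronger readings are tempting and are not supported:

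- **That most measured recognition is created by the survey.** That needs a large returnee share and near-complete recall. The documents give neither figure.
- **That the stigma and acceptance hypotheses fail too.** HCS-CES H3 and H4 do not use recognition. They face only ordinary panel conditioning and a changing mix of volunteers. Nor does any HCS-CES hypothesis compare recognition between waves, so the Wave 1-Wave 2 gap indicates size and is not the bias of a planned test.
- **That the sample size is undermined.** Positive correlation between a person's repeated answers would reduce the variance of change, so treating samples as independent is conservative on that point.
- **That the Protocol already forbids repeat participants.** Table 10 does say, for launch-message testing, "These focus groups may be repeated for subsequent communication campaigns but will not include the same participants". Other formative instruments in that table may be repeated with no such bar, and none of them is the CEQ. It is only an analogy.

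**Conclusion.** The concern holds in a limited form. The plan permits re-survey after messages have been shown and has no rule separating returnees from first-time respondents. Recognition and self-reported exposure among returnees therefore partly reflect the survey. HCS-CES H2 and the exposure dose-response analyses can be biased, in a direction that cannot be determined from the documents.

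The size is conditional. It is zero with no returnees. Under the assumptions in step 3 above, the spurious gap at CEQ6 is about 2 to 21 points, or 3 to 34 if Wave 2 saw no earlier messages. These figures use the maximum number of showings, so they describe Campaign 1 messages and panel members who answered every time.

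The point concerns the campaign evaluation only. It does not touch opioid overdose deaths or the SAP's primary analysis.

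**What to change.** 1. Reconcile the statements on panel membership, re-contact, new samples, cross-sectional design and aggregation, and say which respondents enter each analysis.
2. Flag everyone who entered through panel re-contact and record their number of earlier CEQs.
3. For HCS-CES H2 and the dose-response analyses, base recognition and exposure on first-time (non-panel) respondents.
4. Analyse the panel separately for within-person change. For recognition, use only messages not shown to that person before.
5. Report H3 and H4 with and without panel members as a sensitivity analysis.
6. In any future CEQ, add a self-report item on earlier participation. Do not match on email: the Protocol stores addresses apart from the other screener answers, keeps screener responses apart from survey data, and makes surveys anonymous for people who decline both re-contact and the raffle.

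CEQ7 was scheduled for May-June 2023, so for data already collected this is an analysis rule. It costs some completions. It also depends on the entry route having been recorded, which the documents do not describe. People who returned outside the panel cannot be identified in surveys already done, so some contamination would remain.

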### **Measures**

The measures for the proposed surveys (see Table 7) cover 10 areas related to the specific aims and hypotheses of the CES.

**Table 7: Measures by data collection point**

Measure	Baseline Surveys and Initial CEQ	All Subsequent CEQs	Campaign CEQ Post-Tests
HCS Study and Campaign Awareness	X	X	X
Barriers and Knowledge	X	X	X
Personal Stigma	X	X	X
Provider Stigma	X	X	X
Self-Efficacy	X	X	X
Social Distance/Community Stigma	X	X	X
HCS Message Impact		X	X
Behavior	X	X	X
Personal Experience	X	X	X
Demographics	X	X	X

To meet the aims of the CES and test the proposed hypotheses, the following measures are included: (1) initial measures of *recognition* of the HCS and HCS campaign (adaptation), as well as of other major communication campaigns that may be circulating in the treatment and control communities; (2) measures of *barriers* to uptake of MOUD and OEND and *knowledge* about MOUD/OEND (developed and refined by the Communications Workgroup); (3) measures of *personal stigma* (adaptation from work on predictors of depression stigma); (4) measures of *stigma toward MOUD providers* (adaptation); (5) measures of *self-efficacy*; (6) measures of *social distance (community stigma)* as currently approved for the HCS Coalition Baseline Survey, (7) a *message impact scale* that tests perceived message effectiveness (adaptation), (8) measures of *behavior* surrounding OUD, naloxone, and treatment (adaptation) and from the Communications Workgroup, (9) items measuring *personal experience with OUD* (adaptation), and (10) a series of *demographic questions* that directly align with those from the HCS Coalition Baseline Survey. See Figure 9 for a graph of measures by data collection point and instrument.

#### ***Overview of Health Economics Plan for Intervention Protocol***

We will conduct health economics research to determine the incremental costs of startup and ongoing implementation of the CTH. We will combine these cost estimates with data on the reduced number of opioid overdose deaths attributable to the CTH intervention to estimate the cost effectiveness of reducing opioid overdose deaths, yielding an estimate of the additional cost per averted opioid overdose death. We will also develop a microsimulation model that simulates the natural history of OUD and the effects of prevention and treatment methods, and the CTH intervention. Using the inputs and outcomes of the microsimulation model, we will develop an interactive online tool for policy makers and the scientific community that will allow users to select a geographic area and to evaluate the costs and effectiveness of alternative interventions for that particular area.

The initial phase of the project is focused on estimating the costs of the CTH intervention. To estimate these costs, we use an activity-based costing approach that captures the time spent by staff, space and material resources associated with implementing the CTH intervention components, and other direct costs such as medication, transportation, and staff training.

We will estimate the cost of the core components of the CTH intervention: the CE process, the communication campaign, and the ORCCA EBPs. Health economics measures include instruments that estimate the CE costs of the CAB meetings and activities performed by CAB members; the cost of the community coalition meetings; the cost of activities performed by project staff to facilitate the CTH intervention in communities; and the cost of the preparation, planning, and implementation phases of the communication campaign.

The simulation model will draw on cost, outcome, and transition probability data from the literature and the HCS; no additional primary data collection is anticipated for the simulation model.

## 6.2 Fidelity

### 6.2.1 Fidelity Measures for CTH Community Engagement Intervention

We will use several indicators and sources of data to assess the fidelity of how we deliver the CTH intervention and implementation strategies across the Wave 1 communities and Wave 2 communications when they start implementing the CTH. Fidelity broadly defined is “the extent to which an intervention is implemented as intended”. Fidelity constructs include (1) dosage or exposure to CTH using attendance data (2) adherence using the CTH fidelity checklist and meeting minutes (3) quality of delivery using meeting minutes and ethnographic observation (MA only); (4) output of coalitions as measured by production of such activities as a community profile, community action plan, community dashboard and implementing ORCCA-related trainings (5) participant responsiveness to CTH as measured by feedback from coalition members in annual surveys and qualitative interviews and participant feedback forms and (6) any adaptations or modifications to CTH intervention that communities make. Collectively these different measures will help us assess the extent to which CTH intervention was implemented as intended, the quality of implementation and what adaptations/modifications were made to inform the refinement and dissemination of the intervention if it is found to be effective on study outcomes. If the CTH intervention is for some reason not found to be effective, the fidelity measures will help us understand to what extent the lack of fidelity to CTH may have contributed to the failure to detect significant effects.

The primary source of data will be the CTH Milestone and Benchmark Checklist, which asks the level to which each activity of CTH CE is completed successfully. Responses are coded on a five-point Likert scale: 4=completed, 3=mostly achieved, 2=somewhat achieved, 1=just began, and 0=not started yet. The checklist also asks participants to indicate whether they completed the activity before the CTH CE intervention or during the CTH intervention, what barriers and facilitators hindered or helped their ability to complete the activity, and whether they made adaptations or modifications to the activity. During qualitative interviews, community coalition members will also be asked about challenges they are experiencing adhering to certain CTH CE activities and whether they have made adaptations to certain activities. Another key source of data includes regular review by the study team of coalition meeting minutes and documents of key outputs from CTH CE activities to identify the level to which certain activities are completed; barriers and facilitators to completing certain activities and the extent to which different members of the coalition attend meetings and contribute to the completion of activities; and whether participation in certain activities varies by gender, race, age, educational attainment, or geographic status. The study team will review qualitative interviews, meeting minutes, attendance records of meetings, and anonymous coalition participant evaluation forms to examine the extent to which all members are engaged in decision making, share common goals and objectives, engage in mutually reinforcing activities, and can identify and prioritize activities of the coalition that align with the CTH CE intervention. Table 8 specifies the fidelity measures that will be used to assess adherence to the specific activities of the seven phases of CTH and the implementation strategies that will be used to implement CTH.

**Table 8: Fidelity measures and implementation strategies**

Processes and Activities Within Each Phase	Fidelity Measures	Type/Sources of Data	Time Points for Data Collection
Phase 0: Pre-Intervention  Formation of Study CAB, Share information with communities regarding randomization; Landscape Analysis Phase 1 and 2 and Reporting, Training HCS staff on community engagement; Formation of Coalitions	CTH milestone and benchmark checklist for all Phase 1–6 activities		
Phase 1: Getting Started  Establish a structure for working with coalitions (charter); Recruit Champions, Train Community Coalitions, Plan Communication Campaign; Select Priority groups for Campaign; Introduce ORCCA Menu; Discuss Guidebook and Maps with Coalition, Coalition Review of LA Community Assets Data	Meeting minutes and attendance records for all Phase 1–6 activities  Qualitative interviews to identify barriers and facilitators of completing Phase 1–6 activities	HCS CE facilitators  HCS staff	Monthly  Continuous
Phase 2: Getting Organized  Discuss ORCCA Menu Options Develop a shared vision; Commerce and Evaluate Communications Campaign	Repeated partner tool survey  Document review and upload: Landscape reporting from Phases 1 and 2; Charter;	Coalition participants and key stakeholders	After every Meeting  Annually
Phase 3: Community Profiles and Dashboards  Creation of Community Profile 1.0; Creation of Data Dashboard Template; Map existing services to ORCCA Menu	Communication campaign plan and list of priority groups; Community profile, Dashboard template; Mapping of existing sources to ORCCA menu: ORCCA EBP strategy selection; Evaluation of 1st and 2nd communication campaigns: Implementation Plan for ORCCA EBPs		Annually
Phase 4: Community Action Plan  Develop Implementation plan and Implement ORCCA EBP Strategies; Start Implementing EBPs	Coalition member participant evaluation forms		Continuous after document completion
Phase 5: Implement and Monitor EBPs  Continue to implement and evaluate ORCCA EBPs, troubleshoot and provide technical assistance			

Phase 6: Sustainability Planning Build capacity and align resources, training of coalitions through Learning Health Collaborative			
Implementation Strategies	Fidelity Measures	Type/Sources of Data	Time Points for Data Collection
CTH CE implementation strategies  
 
• CTH training of coalition members on CE strategies
 
• CTH technical assistance and supervision on CE strategies
 
• Utilization of Dashboard for planning and implementing CTH CE activities
 
• Group Model Building Implementation Strategy (NY Site Specific)
 
• Use of dashboard and portal data to guide CTH and ORCCA activities
 
	Number and type of CE and ORCCA training and TA activities completed using training and TA forms, including CE supervision via learning health collaborative meetings  Number and type of CTH supervision meetings held  Attendance records of community coalition members and organizations at CTH supervision meetings	Designated community coalition chair or representative	Monthly  Annual  Continuous
	Qualitative interviews and repeated surveys	Coalition members	Annual
	Participant evaluation forms on training, education (site optional)  Participant evaluations of group model building (GMB) Implementation Strategy (NY site specific)  GMB Field Notes (NY site specific)	CTH/CE training, technical assistance and supervision coordinators  Training and TA participants  GMB participants  HCS research staff	Continuous
	Dashboard and/or portal	Dashboard or community portal search and utilization logs	Continuous

Following is a description of the administration of the fidelity measures listed in Table 8.

CTH milestone and benchmark checklist: HCS CE staff hired by the study will be asked to complete the checklist using a REDCap computerized survey on a monthly basis throughout the CTH intervention period (Phase 0 through Phase 6). Staff will log into REDCap every month to report on intervention fidelity. Each RS will send checklist data for their communities that are in the active intervention phase.

Attendance records: HCS staff will take attendance at every regular HCS designated coalition meeting or conference call in each community implementing the CTH intervention. The attendance sheet will list names of participants, their organizations, and their contact information. The project director (PD) or other designated HCS research staff in each community will enter the participant into the REDCap program and report the total number of participants who attended the meeting, the total number invited to the meeting, the total number of organizations represented at the meeting, and the total number of organizations invited to the meeting. After the PD or designated HCS research staff member finishes entering this attendance information into REDCap, they will store the attendance sheet in a folder in a separate locked file cabinet without any research data in their office, or they will scan a PDF of this sheet and save it in a password-protected, encrypted file on their computer. Hard copies and electronic files of attendance sheets with identifying information will be destroyed at the end of the study after quality assurance is completed. Attendance information will also be collected from subcommittee and work group meetings or conference calls that occur outside the regular HCS designated HCS coalition meeting that will include (1) date of meeting/conference; (2) number of attendees at the meeting/conference call; (3) topics covered in the meeting; and (4) length of meeting in minutes.

Meeting minutes: HCS staff will take minutes of every coalition meeting using a template or an existing meeting minute form. Meeting minutes are critical to HCS study outcomes; thus, the research sites have the option to audio and/or video-record coalition meetings held either in-person, web-based/remotely, or via a hybrid approach where some members are in-person and some join remotely. At the beginning of every meeting, HCS staff will apprise coalition members and attendees that they will be taking meeting minutes that will be used for research purposes to better understand how the coalitions are implementing the CTH intervention, to identify barriers and facilitators of implementing CTH, and to identify any adaptation. If applicable, coalition members will also be informed that the meeting will be audio and/or videorecorded for the sole purpose of creating detailed meeting minutes. At the coalition's request, meeting recording(s) can be shared with coalition members. Coalitions may also choose to take their own meeting minutes and/or record their own meetings for internal purposes. HCS staff will let coalition members know that they can ask to have any comments off the record, and those discussions will not be included in the minutes. The coalition will receive a copy of the minutes by email, and coalition members may ask to remove or edit any portion of the minutes. Coalitions have the final say in what type of information is included in their meeting minutes (some do not want members' names associated with comments and questions made during the meeting, while other coalitions do). HCS staff will upload meeting minutes into a REDCap program or a similar secure, electronic environment along with information on the community and the date of the meeting. If the meeting is audio and/or video-recorded, recorded files will be transcribed, and audio and/or video files will be destroyed within 6 months of being transcribed.

The procedures of taking meeting minutes and using them for research purposes will also be described in coalition charters.

CTH document upload and review: Coalitions will be asked to provide electronic copies of selected documents they produce during CTH activities, including community-specific LA and reporting beyond standard format, the coalition charter, the communication campaign plan and list of priority groups, community profile, data dashboard template, mapping of existing sources to the ORCCA menu, ORCCA EBP strategy selection, evaluation of the first and second communication campaigns, and the implementation plan for ORCCA EBPs. HCS research staff will upload documents into the REDCap program or a similar secure, electronic environment. For document upload, HCS research staff will be asked to indicate what type of document, the community coalition, and the date of upload. HCS research staff may later review and evaluate documents to better understand how CTH activities were implemented and to monitor progress of coalitions and provide feedback for quality improvement. The procedures of collecting and using CTH documents for research purposes will also be described in coalition charters.

Coalition member participant evaluation forms: HCS research staff may administer paper copies (or electronic copies if the meeting is held remotely/web-based) of anonymous brief participant evaluation forms to coalition members after meetings to elicit feedback on their level of satisfaction with different aspects of the CTH intervention and conduct of the meeting, as well as their suggestions for improving the meetings in the future. If the meeting is held in-person, participants will be asked to complete forms and place them in a large envelope when they are done. No identifying information or participant ID numbers will be included on the forms. Data from the forms will be entered into a secure REDCap program. After quality assurance is conducted, paper forms will be destroyed.

Training and TA tracking: RSs will be asked to fill out training or TA service forms for CE or ORCCA training and TA activity in Wave 1 communities on a monthly basis. Data from the forms will be entered into a secure REDCap program. After quality assurance is conducted, paper forms will be destroyed. The collected information will support analyses of ORCCA implementation and costing activities.

Coalition dashboard and portal website logs: HCS RSs may download and review logs or archives of data searches and visualizations conducted by coalition members or key community stakeholders to better understand what type of data coalitions are requesting and how they are using data to guide their planning of CTH and ORCCA activities. These logs will be coded by community site ID number and date. Coalition members will be apprised that their data logs and searches will be saved and used for research purposes on search pages of dashboards and website portals. The procedures of collecting and using these logs for research purposes will also be described to dashboard and portal users when they request access.

Portal Functionality Group Interviews: HCS RSs will conduct group interviews with community members and research staff who actively utilize the community portals and dashboards as part of the HCS. These group interviews will inform the RSs about whether and how dashboards have been useful in CTH decision making, whether they are easy to use and understand, whether they will continue to be used and for what purpose(s), and whether and in what capacity the landscape data will continue to be used to populate the HCS dashboards. A short questionnaire will also be administered electronically via REDCap to gather basic

[figure not shown]
sociodemographic information and assess the respondent's satisfaction with using the CTH portal and dashboard.

The Group Model Building (GMB) participant feedback form: This is a brief, semi-structured instrument intended to evaluate GMB participants' ratings of the quality of the workshop's facilitation, content, clarity, and perceived utility. The instrument includes 13 six-point Likert-type items (6=excellent, 5=very good, 4=good, 3=fair, 2=poor, and 1=very poor) and three short-answer items (to capture specific comments about their experience as a participant). The form was adapted from its original version, which was developed by Zimmerman and colleagues. GMB participants will be asked to complete this form by hand after a workshop session. Completed forms will be placed in a large envelope. Forms will be completed anonymously. No identifying information or participant ID numbers will be used. After quality assurance is conducted, paper forms will be destroyed.

Applying lessons learned from group discussions: HCS research sites may hold group discussions with members from the HCS research cores, community coordinators, fiscal agent representatives and others involved in the CTH intervention to gather feedback and lessons learned for process improvement. These discussions may help inform approaches used with HCS communities and will ensure an intentional and inclusive approach. Lessons learned and process improvement strategies may be shared in presentation and publications and may be shared with community organizations for their own program improvement.

